16.11 Immunosuppression following transplantation

Immunosuppression will be managed by the healthcare team according to standard practice at the participating transplant centre. Maintenance immunosuppression will be changed at the discretion of the clinical team according to factors such as serum levels, rejection episodes, renal function, neutrophil count, viral infections and side effects. Details of the immunosuppression and changes to the immune-suppression regimen that the participant receives will be collected on the case report form.

16.12 Removal of the sentinel skin flap

The SSF may be removed from the recipient at any time due to either flap complications or participant request. Flap complications are rare but include ischemia due to vessel thrombosis and persistent rejection that is resistant to treatment. Removal of the skin flap involves a minor procedure under local, regional or general anaesthetic, according to patient choice. During this procedure all donor tissue is removed and the skin closed to leave a longitudinal scar. This procedure will be undertaken at the patients' local centre by the Oxford or local research team and will take approximately 45 minutes.

17 STUDY ASSESSMENTS/PROCEDURES

17.1 Overview

Table 3 shows scheduled assessments including sampling for the study.

Participants will undergo routine clinical follow-up after transplantation as part of standard care for all lung transplant recipients. The relevant participating transplant centres have standard protocols for the management of patients after lung transplantation. In addition, participants who receive a SSF will be given a Skin Flap Information Leaflet. This provides important information about what to look out for on their skin flap after transplantation and what to do if they notice a skin rash developing. During the first year following transplantation, typically, such patients are reviewed in an outpatient clinic at least 10 times in the first 6 months and then 6 times in the second 6 months (this can be more frequent if problems arise). During these visits the usual monitoring and clinical investigations will be performed by the relevant participating centres. These may include full blood count (FBC), renal function tests (U&Es), liver function tests (LFTs), C reactive protein, immunosuppressant levels and donor specific antibodies (DSA). In addition, there may be organ specific investigations such as respiratory function tests, sputum, radiographs, bronchoscopies, bronchoalveolar lavage, bronchial brushings and allograft biopsies.

Trial-specific follow-up assessments/subsequent visits will coincide with usual care follow-up clinic visits.

Table 3: Summary of study assessments.

PROCEDURE	Pre- baseline	Baseline		3 months +/-4WKS	6 months +/- 4 WK	12 months +/- 4WKS	Rejection Event
	On transplant waiting list	Upon donor matching	Day of trans plant				
Screening/eligibility	Х						
Stage 1 consent	Х						
Stage 2 consent		Х					
Final eligibility		X					
check							
Baseline CRF data	X	X					
collection							
Transplant (+/- skin			Х				
flap)							
HRQoL	X			X		Χ	
questionnaires							
(SF-36, EQ-5D-5L, DAS-24)							
Clinical outcome			Х	Х	X	X	X
data collection			^	^	^	^	^
(CRF)							
(CIVI)	Study Sar	nnles					
Recipient lung			Х				
microbiome biopsy							
or bronchial							
brushing*							
Transplanted lung			X ¹	Х	Х	Х	Х
biopsy							
(if and when							
routinely							
performed, centre							
specific)**							
Transplanted lung			Х	Х	Х	Χ	Х
bronchial brushing							
or broncho-alveolar							
lavage or sputum (if							
and when routinely							
performed, centre							
specific)*							
		1	l				 

PROCEDURE	Pre- baseline	Baseline		3 months +/-4WKS	6 months +/- 4 WK	12 months +/- 4WKS	Rejection Event
Skin swab of flap (those randomised to the lung and sentinel skin flap group).			X ¹	X	X	X	Х
Skin flap biopsy (those randomised to the lung and sentinel skin flap group)*			X ¹	Х	Х	Х	Х
Recipient native skin swab microbiome sample (both groups)			X ¹	Х	Х	Х	Х
Blood sample (both groups)			X ¹	Х	Х	Х	Х

^{*}When taken, these samples will be divided into two and sent to both a local lab for immediate analysis and to Oxford for storage for later analysis.

^{**} All biopsies are sent to local lab for analysis until the end of the trial when they will be transferred to Oxford for analyis.

X¹ after transplant re-vascularisation.

17.2 Samples

Refer to SAMPLES FOR LABORATORY ANALYSIS section for full details on study samples, including taking, processing and shipping, where applicable.

17.3 Data Collection

Baseline data

Once Stage 1 consent has been obtained, baseline data collection can commence, including the baseline HRQoL questionnaires (SF-36, EQ-5D-5L and DAS-24). Where possible, baseline questionnaires will be completed electronically by the participant. Paper questionnaires may also be used where use of electronic means is not possible or suitable. Where paper-based questionnaires are used, data will be entered into the study database by the local site research team.

Once Stage 2 consent has been obtained (telephone or in person), further baseline data will be collected. This may be before or after randomisation depending on the time available between Stage 2 consent and the transplant taking place.

Completed at hospital by local study team member from medical notes or with participant prior to transplant

Sourced/collected by local study team	Direct patient report
 Date of baseline visit Participant demographics which will include: Date of birth Sex Height and weight (to calculate BMI) Ethnicity Reason for requiring lung transplant Co-morbidities Contact details of participant Participant's NHS/CHI number 	 Health-related quality of life* SF-36 (unmodified) EQ-5D-5L (unmodified) DAS-24 (unmodified)
Collected after transplant: Transplant outcome Date of transplant Skin flap transplant details to include: Location of transplanted flap Operating time/duration Reason for not receiving a transplant or not receiving the sentinel skin flap (if randomised to skin flap arm) Transplant type Organs transplanted Details of donor matching^ Donor age, sex and weight^ Cold ischaemia time (lung) Operating time/duration	

•	Details of induction and regular
	immunosuppression
•	Surgical complications
•	Bionsy results

Completed by dedicated skin flap retrieval and transplant team after transplant

Sourced/collected by local study team

- Details of skin flap retrieval which will include:
 - o Skin flap retrieval outcome
 - o Skin flap transplanted
 - o Reason for non-transplant
- Presence of an arterial line prior to skin flap retrieval.

Follow-up data

3 months post-transplantation

Sourced/collected by local study team	Direct patient report
 Surgical complications relating to the SSF Biopsy-proven or clinical rejection Transplant organ function Antibodies Immunosuppression Check that lung and/or skin biopsy samples have been collected and sent for clinical analysis and storage at the participating sites pathology labs until the end of the trial when they will be transferred to Oxford for the mechanistic work. Check that blood and microbiological swabs and half of the skin biopsy have been collected and sent to Oxford for storage for later analysis. Graft and patient survival 	Health-related quality of life* SF-36 (unmodified) EQ-5D-5L (unmodified) DAS-24 (unmodified)

6 months post-transplantation

Sourced/collected by local study team	Direct patient report
Surgical complications relating to the SSF	N/A
Biopsy-proven or clinical rejection	
 Transplant organ function 	

SENTINEL_Protocol_V1.1_27Apr2023.docx IRAS number: 318347 REC Reference: 23/LO/0248

[^] information regarding the donor matching accompanies the transplanted organ(s). Further information regarding the donor (age, sex and weight) is collected routinely by NHSBT and will be accessed by the research team from the medical notes.

		T
•	Immunosuppression levels and	
	requirements	
•	Check that lung and/or skin biopsy	
	samples have been collected and sent	
	for clinical analysis and storage at the	
	participating sites pathology labs until	
	the end of the trial when they will be	
	transferred to Oxford for the	
	mechanistic work.	
•	Check that blood and microbiological	
	swabs and half of the skin biopsy have	
	been collected and sent to Oxford for	
	storage for later analysis.	
•	Graft and patient survival	

12 months post-transplantation

Sourced/collected by local study team	Direct patient report
 Surgical complications relating to the SSF Biopsy-proven or clinical rejection Transplant organ function Immunosuppression levels and requirements Check that lung and/or skin biopsy samples have been collected and sent for clinical analysis and storage at the participating sites pathology labs until the end of the trial when they will be transferred to Oxford for the mechanistic work. Check that blood and microbiological swabs and half of the skin biopsy have been collected and sent to Oxford for storage for later analysis. Graft and patient survival 	Health-related quality of life* SF-36 (unmodified) EQ-5D-5L (unmodified) DAS-24 (unmodified)

^{*}Patients will be sent HRQoL questionnaires via e-mail or post (depending on participant preference) at baseline, 3 months, and 12 months post-randomisation, with an option to be contacted by telephone by the Surgical Intervention Trials Unit (SITU).

Upon detection of a rejection event:

Sourced/collected by local study team	Direct patient report
Method of diagnosis (clinical/biopsy)Reason for suspecting rejection	N/A
 Investigations for rejection 	
 Biopsies taken and results 	

SENTINEL_Protocol_V1.1_27Apr2023.docx IRAS number: 318347 REC Reference: 23/LO/0248

- Check that lung and/or skin biopsy samples have been collected and sent for clinical analysis and storage at the participating sites pathology labs until the end of the trial when they will be transferred to Oxford for the mechanistic work.
- Check that blood and microbiological swabs and half of the skin biopsy have been collected and sent to Oxford for storage for later analysis.
- Treatment of rejection event
- Resolution date

17.4 Assessments for investigating signs of rejection

Certain events that indicate possible rejection will trigger an additional visit and procedures. These events are:

- Skin rash/ oedema on sentinel skin flap confirmed as rejection
- Clinically significant drop in lung function on spirometry
- Clinically significant change in chest x-rays
- New symptoms suggestive of rejection such as cough, breathlessness, fever

17.5 Qualitative assessments

No qualitative research will be performed as part of the trial.

17.6 Withdrawal of Participants

Withdrawal of consent means that a participant has expressed a wish to withdraw from the study altogether or from different aspects of the study.

Data and samples collected up to the point of withdrawal will be used in the study analysis. For complete withdrawal from the study: Under these circumstances, the site needs to document all relevant discussions in the participant's medical notes. No subsequent data (including routine care data) should be captured in the CRF. The site should notify the SENTINEL study office, which will allow them to mark all future CRFs as not applicable. However, under these conditions, investigators are still responsible for following up any SAEs, and should continue to report the SAE to resolution in the CRF and to the study centre.

For withdrawal from different aspects of the study participants can decide which aspects of the study they wish to stop participating in.

The type of withdrawal will be collected on the CRF.

The following types of withdrawal will be captured within the CRF with appropriate action taken by the study to ensure compliance with the participant's wishes:

- No longer willing to complete study questionnaires
- No longer willing to provide study samples
- No longer willing to receive study-related communications
- No longer willing to attend study visits
- No longer willing to be contacted by the research team to obtain outcome data

 No longer willing to have intervention (Skin-flap) (Request for participant to have skin flap removed)

17.7 Withdrawal of participant by the clinician

Withdrawal from the study or parts of the study may come from clinicians if they believe the participant needs to be withdrawn. Under these circumstances, the site needs to document the reason for the clinician's withdrawal of the individual in the participant's medical notes. The site should notify the SENTINEL study office, which will allow them to mark all future CRFs as not applicable. However, under these conditions, investigators are still responsible to follow up any SAEs, and continue to report the SAE to resolution in the CRF and to the study centre.

The type of withdrawal will be collected on the CRF.

Data and samples collected up to the point of withdrawal will be used in the study analysis.

17.8 Participants that do not proceed to transplant

Participants who consent to be included in the study may not proceed to transplantation during the study period as:

- 1) they may not receive an offer of an organ;
- 2) may become too unwell or die;
- 3) may recover and no longer need transplantation.

17.9 Participants that are offered a transplant where skin has not been agreed to be also donated

Participants who consent to be included in the study may proceed to transplantation but not be randomised. If an organ is only offered for donation without skin – a matched individual will be offered the organ and if they take the transplant offer up – and it proceeds this will end their participation in the study. A thank you letter will be sent to the individual at this point.

17.10 Participants that are offered a transplant where skin is available and to which they are randomised to an SSF with their transplant but they do not receive the SSF but they still receive the lungs

Participants who consent and are randomised may not receive their allocation as the transplant fails to proceed as the lung donation is found to be inadequate for transplantation, or the skin flap is found inadequate for transplantation.

If the lung is not transplanted these participants will return to the lung transplant waiting list and will not be replaced.

If the lung is transplanted but the skin flap is not transplanted, these patients will cross over to the lung only arm of the trial.

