16.5 Lung transplantation with skin sentinel flap transplant (intervention)

Participants randomised to receive lung transplantation with an additional SSF transplant will receive a SSF from the same donor as the lung, at the same time as the lung transplant. The SSF (10cm x 3cm) will be anastamosed onto the ulnar artery of the recipient's non-dominant forearm at the same time as lung transplantation. The two procedures will be performed simultaneously to ensure that total operative and anaesthetic time is not prolonged. The arm will be abducted away from the body onto an arm table or anaesthetic arm board, to avoid interference with the lung transplant team. Inset of the forearm skin

flap takes 1-2 hours. Lung transplantation takes an average of 4-12 hours, depending on the complexity of the procedure.

In the unlikely event that there is an anatomical or personal reason that a SSF cannot be anastomosed onto the non-dominant forearm, then it can be implanted onto their dominant forearm. Alternatively, another site, such as the groin or axilla can be chosen, or the participant can be withdrawn from the study. The options will be described within the patient information sheet and discussed and confirmed with the patient pre-operatively.

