16.7 Sentinel skin flap retrieval

If a suitable donor, with consent obtained for both lung and skin donation is matched with a patient, their local participating site will be informed (in accordance with NHSBT procedures). The dedicated retrieval team will be contacted by the participating site to ensure availability for skin retrieval, as there may be situations where transplantation procedures are already underway elsewhere and retrieval of the skin flap is not possible. If the patient confirms their consent to take part in the study, they will be randomised. If they are randomised to receive a SSF, the dedicated retrieval team will be placed on standby to travel to the donor hospital to retrieve the SSF alongside the usual lung retrieval team.

If skin flap retrieval is not possible or viable then lung retrieval and transplantation will proceed as planned without skin flap transplantation.

Where a skin flap is retrieved and not transplanted, the NHSBT will be informed and the skin flap will be discarded or used in other research approved by NHSBT provided the family has consented for such use. The study database will record that the skin flap was retrieved and not used. Skin flaps not used for the purpose of this study will be tracked and documented within NHSBT systems to ensure that they are handled and managed appropriately and in accordance with relevant approvals.

In the unlikely event that two donations are approved at the same time, and the skin flap retrieval team are not available to retrieve both SSFs, then the donation logistically/geographically nearest to the retrieval team would take priority; and only that recipient randomised. If that recipient randomises to lung only then the second recipient may be randomised.

Rarely, a skin flap may be required for both a lung transplant, as part of this study, and a intestinal transplant, as part of another study. In this instance, the SSF will be split in two for each recipient or prioritised for the intestinal transplant.

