24.4 Description of Statistical Methods

Results will be reported in line with the CONSORT statement and relevant extensions (41)(42).

All outcomes will be summarised using descriptive statistics overall and, when collected for both arms, split by treatment groups. Binary and categorical data will be summarised by frequencies and percentages. Continuous data will be summarised by means and standard deviations (SDs), or median and inter-quartile range if data are skewed. Corresponding 95% confidence intervals will be presented where possible. Visual representation of outcomes will be considered and, where it will support interpretation, presented.

Analysis will be conducted using a complete case approach, no imputation methods for missing data are planned. Analysis of the primary and secondary outcomes will be done once the 12 month follow up has been reached by the last patient. Analyses of these outcomes will be pre-specified in a statistical analysis plan finalised prior to un-blinding of the data. Analysis of mechanistic outcomes, using sample data, will be done following completion of the primary and secondary outcomes.

An independent Data and Safety Monitoring Committee (DSMC) will meet early in the trial to agree its terms of references. They will review confidential interim analyses of accumulating data, including the interim analysis of the stop-go criteria and diagnostic accuracy.

It is anticipated that all statistical analysis will be undertaken using Stata (StataCorp LP, www.stata.com) or other well validated statistical software.

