24.9 Inclusion in analysis

The principle of intention-to treat (ITT), as far as practically possible will be the main strategy for the primary outcome and all secondary outcomes (except for Secondary Outcome 2d). ITT will analyse all randomised and transplanted patients, in the group to which they were allocated and for whom the outcomes of interest have been

observed/measured. To check the robustness of analysis under ITT, a secondary sensitivity per-protocol analysis, which will mirror the ITT population but exclude participates defined with a major protocol deviation, will be conducted. Secondary outcome 2d (safety events) will be analysed according to the safety population, which will include all participants who receive a transplant, where groups are defined according to whether or not they received a skin transplant.

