24.14 Procedure for accounting for missing, unused and spurious data

The procedure for handling spurious or missing data will be described in the SAP. The trial will attempt to collect data as completely as possible.

The main analysis will include participants for whom endpoint data are available, with other participants being censored after their last available relevant outcome measure. It is anticipated that there will be minimal participant attrition. The sample size calculation has been adjusted to account for loss to follow-up or patient death.

24.15 Procedures for reporting any deviation(s) from the original statistical analysis plan Any deviation(s) from the original SAP will be described in the final report.

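### Section 17.10 sends flap-allocated participants without a flap to the lung-only arm, against section 24.9, and sections 16.5 and 17.7 could end their outcome follow-up

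*Protocol*

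**What the plan says.** Five parts of the protocol bear on a participant allocated to lung plus flap who ends up without a flap.

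- **Section 16.7** lets the lung transplant go ahead and is silent on trial status: "If skin flap retrieval is not possible or viable then lung retrieval and transplantation will proceed as planned without skin flap transplantation".
- **Section 17.10** assigns a status to those who receive the lung but not the flap: "these patients will cross over to the lung only arm of the trial".
- **Section 16.5** covers flap-allocated participants for whom an anatomical or personal reason rules out the non-dominant forearm. After offering the dominant forearm it continues: "Alternatively, another site, such as the groin or axilla can be chosen, or the participant can be withdrawn from the study". It does not say which kind of withdrawal is meant.
- **Section 17.7** provides for clinician-led withdrawal: "Withdrawal from the study or parts of the study may come from clinicians if they believe the participant needs to be withdrawn". Later CRFs are then marked not applicable, serious adverse events remain the only stated follow-up, and data already collected are kept.
- **Section 24.9** defines the primary analysis set: "ITT will analyse all randomised and transplanted patients, in the group to which they were allocated", limited to those whose outcome was observed. Only safety outcome 2d is grouped by whether a flap was received.

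On missing data, section 24.4 states "Analysis will be conducted using a complete case approach, no imputation methods for missing data are planned". Section 24.14 includes participants with endpoint data, "with other participants being censored after their last available relevant outcome measure".

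**The concern.** A control participant has no flap to lose. Moving between arms under 17.10 and withdrawal for a placement problem under 16.5 can therefore affect the flap arm only. Both happen after randomisation, when participants and site staff know the allocation (section 15.7). If the reasons for having no flap are related to rejection risk, either step makes the arms differ for a reason other than the flap.

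Loss of follow-up is harder to repair than the label. A statistician can restore the allocated group at analysis, but cannot analyse 12 months of outcomes that were never entered. Section 9.2 takes the primary outcome from medical notes and histology reports, so the information would usually exist in routine records even when the trial had stopped collecting it.

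**Working it through.** **The texts side by side.** For a flap found inadequate or not retrieved, the competing rules are 17.10 (lung-only arm) and 24.9 (allocated arm). For an anatomical or personal placement problem, 16.5 adds possible withdrawal. Section 17.7 applies to both arms and is not triggered by a missing flap, but it shows what a non-consent withdrawal does to data collection. None of these sections refers to another, and none says that crossing over describes treatment received only.

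**The plan's own figure.** Inputs from section 24.2: control risk p1 = 0.80, flap risk p2 = 0.5333, two-sided 5%, 90% power. With pooled variance and no continuity correction:

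n per arm = [1.96 × √(2 × 0.6667 × 0.3333) + 1.2816 × √(0.80 × 0.20 + 0.5333 × 0.4667)]² / 0.2667² = (1.307 + 0.819)² / 0.0711 = 63.6, so 64 per arm and 128 in total. Dividing by 0.85 gives 75.3, so 76 per arm and 152. Both stated figures reproduce; this point is not about arithmetic in the plan.

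**Illustration 1: no true effect.** Let x be the share of the flap arm without a flap and r their 12-month rejection risk. Both are assumptions. The flap arm as allocated has 80% risk.

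- Risk in those left in the flap arm: (0.80 − x·r)/(1 − x)
- Risk in control after receiving the moved patients: (0.80 + x·r)/(1 + x)
- Shift if moved: the second minus the first. Shift if withdrawn: 0.80 minus the first.

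For x = 10%, r = 100%: remaining flap arm 0.70/0.90 = 77.8%; enlarged control 0.90/1.10 = 81.8%. Moving gives 81.8 − 77.8 = +4.0 points; withdrawing gives 80 − 77.8 = +2.2. A positive sign is a spurious benefit of the flap.

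| x | r | Moved | Withdrawn |
|---|---|---|---|
| 5% | 100% | +2.0 | +1.1 |
| 5% | 60% | −2.0 | −1.1 |
| 10% | 100% | +4.0 | +2.2 |
| 10% | 80% | 0 | 0 |
| 10% | 60% | −4.0 | −2.2 |
| 20% | 100% | +8.3 | +5.0 |
| 20% | 60% | −8.3 | −5.0 |

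The target difference is 26.67 points. At x = 10% and r = 100%, the approximate two-sided type I error with 64 per arm is 9% if moved and 6% if withdrawn. The withdrawn column treats these patients as fully removed, so it is an upper bound: data before withdrawal are kept and act as early censoring. For a failure of placement at surgery, little follow-up would precede withdrawal.

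**Illustration 2: flap effective, no-flap patients at the control risk of 80%, x = 10%.** As allocated, the flap-arm risk is 0.9 × 0.5333 + 0.1 × 0.80 = 0.56, a difference of 24.0 points and power of 84%. Withdrawn: 26.7 points on about 58 versus 64, power 89%. Moved: 26.7 points on about 58 versus 70, power 90%. The rules therefore estimate different quantities even when no-flap patients have the same risk as controls.

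**The case against.** The strongest defence is that 24.9 is the only section that defines analysis groups, and it does so correctly. It already separates allocation from receipt, since only outcome 2d follows the flap received. Section 17.10 sits among study procedures, where crossing over can mean the treatment given. This stands. A reader might infer that the protocol breaks intention-to-treat; the text does not establish that. The breach would follow only if 17.10 were applied to the analysis groups.

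Other stronger readings also fail:

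- **Three rules collide for every no-flap patient.** Section 16.5 is optional, is described as unlikely to be needed, concerns placement rather than flap quality, and is discussed before surgery. The three rules meet only in that subset.
- **Withdrawn patients are deleted.** Sections 17.6 and 17.7 keep earlier data, and section 9.2 requires the withdrawal date for the primary outcome. The effect is early censoring, possibly informative.
- **Complete-case handling drops those who die or leave before rejection and keeps early rejectors.** Read literally, 24.4 and 24.9 permit this. But 24.5 specifies a Cox model of time to first rejection, 9.2 collects death and withdrawal dates, and 24.14 censors. The intention appears to be censoring; the wording needs aligning.
- **The bias favours the flap.** Nothing in the documents fixes its direction.

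The share without a flap may also be small: skin donation is confirmed before randomisation (16.3), retrieval-team availability is checked (16.7), and severe peripheral vascular disease with no usable vessels is an exclusion (12.4).

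What survives is that sites act on sections 16 and 17, and these point them away from 24.9. A later analysis plan can settle labels but cannot recover data that were not collected.

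**Conclusion.** The concern holds as an inconsistency with a conditional consequence. Section 17.10 contradicts 24.9 on the status of flap-allocated participants who receive lungs only, and 16.5 with 17.7 opens a route by which non-placement ends outcome collection without withdrawal of consent. If 17.10 governed the analysis groups, or follow-up stopped at non-placement, the flap arm alone would lose patients or be censored early.

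The size cannot be stated from the documents. Under the null and an assumed 10% share, the shift runs from about −4 to +4 points if patients are moved and −2.2 to +2.2 if withdrawn, as their assumed risk runs from 60% to 100%. It is zero only if their risk equals that of the rest of the arm. These shifts are small beside 26.67 points, but avoidable. The plan's sample size arithmetic is unaffected.

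**What to change.** 1. **Section 17.10.** State that these participants received lung-only treatment, remain in the SSF arm for the intention-to-treat analysis and are followed for 12 months. Record flap receipt for the safety (2d) and per-protocol sets.
2. **Sections 16.5 and 17.7.** Reconcile both with 24.9, so that neither non-placement of the flap nor clinician withdrawal by itself ends collection of outcome data from routine notes unless the participant withdraws consent. The placement options themselves stay as they are.
3. **Sections 24.4 and 24.9.** Align the complete-case wording and the observed-outcome condition with 24.14: time-to-event outcomes include every randomised and transplanted participant, censored at last available follow-up.

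The cost is a few sentences and minor extra data entry from notes. The intention-to-treat effect is slightly diluted. If no-flap patients carry the control risk, power falls from 90% to about 87% at an assumed 5% share and 84% at 10%; section 24.2's allowances cover loss, death and non-transplant, not this. The change should come before affected cases accrue, because missed follow-up may not be recoverable.
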